6.2.12. Number of COVID-19 Related Medical Visits

The number of COVID-19 related medical visits will be analyzed with a negative-binomial regression model, using the log-total number of days of data collection as the participant offset variable. The resulting analysis will show the difference in estimated rate of medical visits between treatment groups. The analyses will be done using mITT, mITT1, and mITT2 populations.

6.2.13. Number of Days in Hospital and ICU Stay in Participants with COVID-19 Related Hospitalization

Health resource utilization data will be summarized by treatment group. This will include number (days) of hospital stay and number (days) of ICU stay. The analyses will be done using mITT, mITT1 ,and mITT2 populations. Descriptive statistics (ie, mean, median, range) will be used to summarize this endpoint.

CCI			

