•	To describe the viral load in nasal samples over time in nonhospitalized symptomatic adult participants with COVID-19 who are at increased risk of progression to severe disease.	
 
Viral titers measured via RT-PCR in nasal swabs over time.
 
	• Not applicable.

Objectives		Endpoints	Estimands
•	To compare PF-07321332/ritonavir to placebo for COVID-19-related medical visits in nonhospitalized symptomatic adult participants with COVID-19 who are at increased risk of progression to severe disease.	• Number of COVID-19 related medical visits through Day 28.	• Not applicable.
•	To compare PF-07321332/ritonavir to placebo for COVID-19-related hospitalizations in nonhospitalized symptomatic adult participants with COVID-19 who are at increased risk of progression to severe disease.	• Number of days in hospital and ICU stay in participants with COVID-19 related hospitalization.	• Not applicable.

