2.1.2. Secondary Estimands

The estimand associated with the key secondary efficacy objective is the difference in proportions of patients experiencing COVID-19-related hospitalization or death from any cause through Day 28 in nonhospitalized adult patients with symptomatic COVID-19 who are at increased risk of progression to severe disease and who did not receive COVID-19 therapeutic mAb treatment. This will be estimated without regard to adherence to randomized treatment.

The estimand associated with the secondary efficacy objective regarding the duration and severity of signs and symptoms is the absolute difference in median time to sustained alleviation or resolution of symptoms for all nonhospitalized adult patients with COVID 19 who are at increased risk of progression to severe disease. This will be estimated irrespective of adherence to randomized treatment.

The hospitalization/death rate through Day 28 is considered the main clinical outcome measure and signs/symptom duration is considered key secondary for this study and so estimands for these measures are presented. Estimands for the other outcome measures that are considered supportive of the primary outcome measures and of the sign/symptoms duration and severity outcome measure are not presented.

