3.2. Secondary Endpoint(s)

- The first key secondary efficacy endpoint is the proportion of participants with COVID-19 related hospitalization or death due to any cause through Day 28 in the mITT1 analysis set.
- Incidence of treatment emergent adverse events (TEAEs).
- Incidence of SAEs and AEs leading to discontinuations.
- *Time (days) to sustained alleviation of all targeted signs/symptoms through Day 28.*
- Proportion of participants with severe signs/symptoms attributed to COVID-19 through Day 28.
- *Time (days) to sustained resolution of all targeted signs/symptoms through Day 28.*

- Duration of each targeted COVID-19 sign/symptom.
- Progression to a worsening status in 1 or more self reported COVID19 associated symptoms through Day 28.
- *Proportion of participants with a resting peripheral oxygen saturation* ≥95% *at Days 1 and 5.*
- Proportion of participants with death (all-cause) through Week 24.
- *PF-07321332 PK in plasma and whole blood (if feasible).*
- Viral titers measured via RT-PCR in nasal swabs over time.
- Number of COVID-19 related medical visits.
- Number of days in hospital and ICU stay in participants with COVID-19 related hospitalization.

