5.2.4. Analyes for Count Endpoints

For count endpoints (ie. number of COVID-19 related medical visits and number of hospitalizations/ICU visits), a negative binomial regression model analysis, using the log total number of days of data collection as the participant offset variable, will be conducted and the difference in estimated rate will be provided.

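### Hospital and ICU days are summarized by arm only among hospitalized participants, so the means are not a randomized comparison; add an all-participant summary

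*SAP*

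**What the plan says.** Protocol Section 3 states the objective as a treatment comparison: "To compare PF-07321332/ritonavir to placebo for COVID-19-related hospitalizations in nonhospitalized symptomatic adult participants". The endpoint attached to it, repeated in SAP 3.2, is narrower: "Number of days in hospital and ICU stay in participants with COVID-19 related hospitalization". The estimand column for this row reads not applicable. SAP 2.1.2 confirms the gap more generally: "Estimands for the other outcome measures that are considered supportive of the primary outcome measures" are not presented.

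The heading of SAP 6.2.13 carries the same restriction: "Number of Days in Hospital and ICU Stay in Participants with COVID-19 Related Hospitalization". Under it the SAP summarizes "number (days) of hospital stay and number (days) of ICU stay" by treatment group for mITT, mITT1 and mITT2, and adds: "Descriptive statistics (ie, mean, median, range) will be used to summarize this endpoint". SAP Appendix 1 also lists the analysis as descriptive, without imputation.

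Neither document says that a participant who was never admitted counts as zero days. Neither says how to treat a stay that ends in death, and the endpoint has no time limit.

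**The concern.** Hospitalization is a post-randomization event and part of the primary endpoint. Protocol 2.3.2 names its prevention as a potential benefit, and the sample size assumes that hospitalization or death is halved. The hospitalized participants in the two arms are therefore selected by different processes. If the drug prevents mainly the shorter admissions, those that remain on active are the longer ones, and the mean stay rises although nobody was harmed. If it prevents mainly the longer ones, the mean stay falls although no remaining stay was shortened. Without an estimand, nothing tells a reader of the by-arm means that they do not measure a drug effect on hospital use. The quantity that randomization does protect, days in hospital per participant, is not planned.

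**Working it through.** **1. The plan's own figure.** Inputs from Protocol 9.5: placebo 7%, difference 3.5 points (so active 3.5%), 90% power, two-sided 5%. Allocation is 1:1 (Protocol 4.1). With the pooled-variance formula:

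n per arm = [1.960 × √(2 × 0.0525 × 0.9475) + 1.282 × √(0.07 × 0.93 + 0.035 × 0.965)]² / 0.035² = 852, or 1704 in total.

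The plan states 1717, which is close; the small excess fits one O'Brien-Fleming interim look. Power at 1717 is 90.2%. The design rates are therefore a fair basis for sizing the subset.

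**2. Size of the hospitalized subset in mITT.** 1717 / 2 = 858.5 per arm.
- Placebo: 858.5 × 0.07 = 60.1.
- Active: 858.5 × 0.035 = 30.0.

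Both are upper bounds, because the rates also include deaths without admission. Together they are (60.1 + 30.0) / 1717 = 5.25% of the set.

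**3. Illustration of the selection effect.** The documents give no lengths of stay, so these are assumptions. Treat 7% and 3.5% as admission rates. On placebo, half of the admissions last S days (4 to 7) and half last 14. The drug prevents half of all admissions and changes no stay that still occurs. Let f be the share of prevented admissions that are short.

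- Mean stay among the hospitalized, placebo: (S + 14) / 2.
- Mean stay among the hospitalized, active: (1 − f) × S + f × 14.
- Difference, active minus placebo: (f − 0.5) × (14 − S).
- Days per 100 participants: 7 × placebo mean, and 3.5 × active mean.

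| S | f | Mean stay, placebo | Mean stay, active | Difference | Days per 100, placebo | Days per 100, active |
|---|---|---|---|---|---|---|
| 4 | 0.50 | 9.0 | 9.0 | 0.0 | 63.0 | 31.5 |
| 4 | 0.75 | 9.0 | 11.5 | +2.5 | 63.0 | 40.3 |
| 4 | 1.00 | 9.0 | 14.0 | +5.0 | 63.0 | 49.0 |
| 7 | 0.50 | 10.5 | 10.5 | 0.0 | 73.5 | 36.8 |
| 7 | 0.75 | 10.5 | 12.25 | +1.75 | 73.5 | 42.9 |
| 7 | 1.00 | 10.5 | 14.0 | +3.5 | 73.5 | 49.0 |

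Days per 100 participants fall in every row by construction, since the drug only removes admissions here. The hospitalized-only mean is unchanged or longer.

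**4. The other direction.** With S = 4 and f = 0.25, the difference is (0.25 − 0.5) × 10 = −2.5 days, so 6.5 on active against 9.0 on placebo. The drug appears to shorten stays although it shortened none.

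**5. What an all-participant summary looks like.** At design rates at least 93% of placebo and 96.5% of active participants have zero days. The median is zero in both arms, so the mean has to carry the comparison.

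**The case against.** The strongest reply is that nothing inferential hangs on this table. SAP 6.2.13 plans no model, test or confidence interval. The endpoint is in neither the sequential tests nor the Hochberg list in SAP 5.1, and the heading openly names the restriction. The effect on admissions is measured without conditioning by the primary endpoint in mITT and its mITT1 and mITT2 versions. The medical-visit rate, which covers hospitalizations (Protocol 8.1.2), is modelled in the same sets. A reader would therefore see fewer admissions beside any longer mean stay. All of this stands and keeps the point minor. It does not close the gap: neither analysis reports days in hospital, and the objective is still worded as a comparison. Naming the mITT sets in 6.2.13 leaves some ambiguity, but without a zero-day rule the heading governs.

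A reader might also infer that SAP 5.2.4 contradicts 6.2.13, because it plans a model for "number of hospitalizations/ICU visits), a negative binomial regression model analysis". It does not. That text concerns counts of hospitalizations and ICU visits, whereas 6.2.13 concerns days. A model for one and a descriptive summary for the other can coexist.

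**Conclusion.** The point holds, at low priority. The by-arm mean hospital and ICU days in SAP 6.2.13 describe at most about 60 placebo and 30 active mITT participants, selected after randomization, and cannot serve the objective of comparing the arms. Under the assumptions in the working, with 50% to 100% of prevented admissions short, the mean stay would be 0 to 5 days longer on active while days per 100 participants fall from 63–73.5 to 31.5–49. Those lengths of stay are assumed, and so is a drug that only removes admissions.

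Two stronger readings are tempting. One is that the table will make a beneficial drug look harmful. The documents do not support a direction: the distortion is zero when short and long stays are prevented equally, and it favors the drug when mainly long stays are prevented. The other is that a formal treatment comparison is invalid. No such comparison is planned, so the primary analysis and type I error are untouched.

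**What to change.** In SAP 6.2.13, with a matching row in Appendix 1:

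- Add a summary of hospital days and of ICU days through Day 28 over all participants in mITT, mITT1 and mITT2, counting zero for those not admitted. Report mean days per participant (or per 100 participants) and the between-arm difference, because the median will be zero.
- Show deaths through Day 28 in the same table, and state in advance how a stay ended by death is counted. Otherwise an early death reads as a short stay.
- Keep the hospitalized-only table, without a Day 28 cut-off, labelled as descriptive and not a treatment comparison.

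The cost is SAP wording and one extra table. Protocol 8.1.2 already collects admission and discharge dates and ICU status, so no new data are needed. The downside is that stays running past Day 28 are truncated in the new summary; the retained table still shows them in full.

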6.4. Subset Analyses

For the primary endpoint, forest plots for the following subgroups on mITT, mITT1 and mITT2) will be presented.

PFIZER CONFIDENTIAL
Page 28

Subgroup analyses of the primary endpoint will include:

- age group (<65, >=65);
- Gender;
- Race;
- BMI category (<25, 25-29, ≥30);
- Baseline viral load (<10⁴ copies/mL, \geq 10⁴ copies/mL) and (<10⁷ copies/mL, \geq 10⁷ copies/mL);
- Baseline serology status (positive, negative);
- Number of baseline comorbidities present (0-1, 2-3, >=4);
- Viral strain/linage at Day 1 if appropriate;
- Present of any of these baseline comorbidities/risk factors:
 - Smoking (yes, no);
 - Diabetes mellitus;
 - Immunosuppression disorders (including use of corticosteroids, biologics or those undergoing chemotherapy);
 - Chronic lung disease requiring medication;
 - Hypertension (taking medications for hypertension);
 - Cardiovacular disorders;
 - Chronic kidney disease;
 - HIV Infection;
 - Sickle Cell Disease;
 - Neurodevelopmental Disorder;
 - Cancer;
 - Device Dependence.

For a particular risk factor to be summarized, a minimum of 100 subjects in risk group is required. The sub-group analysis will be performed for mITT and mITT1 populations.

6.5. Baseline and Other Summaries and Analyses

6.5.1. Baseline Summaries

The demographic characteristics will be summarized by treatment group within the FAS. This will include age, gender, race, baseline height, and baseline weight. All baseline disease characteristics will be summarized by treatment group within the FAS.

6.5.2. Study Conduct and Participant Disposition

Participant evaluation groups will be presented for all screened participants, and participant disposition will be summarized within the FAS population. The number of participants screened and randomized will be presented. The number of participants, treated, completing and discontinuing by study phase, as well as the number of participants in each analysis set will be summarized by treatment group. For participants who did not complete the study, the reasons for withdrawal from the study will be presented.

In addition, the number of participants who were excluded from the PPanalysis set will be summarized by reasons for the exclusion.

6.5.3. Study Treatment Exposure

Duration of treatment will be summarized within SAS population.

The duration of treatment will be calculated as follows:Duration of treatment = Date of last dose of study drug - date of first dose of study drug +1.

6.5.4. Prior and Concomitant Medications

The frequency of prior and concomitant medications will be summarized by treatment based on the WHO-drug coding dictionary within SAS population in accordance with Clinical Data Interchange Standards Consortium (CDISC) and Pfizer Standards (CaPS).

6.6. Safety Summaries and Analyses

Standard summary tables and listings will be generated in accordance with Clinical Data Interchange Standards Consortium (CDISC) and Pfizer Standards (CaPS) for safety reporting for the following parameters: adverse events, lab parameters, vital signs, discontinuations from study, discontinuations from treatment, and treatment duration.

6.6.1. Adverse Events

All adverse events will be coded according to the Medical Dictionary for Regulatory Activities (MedDRA) and will be summarized by treatment group within SAS population. Only TEAE summaries to AEs that started on or prior to Day 34 will be summarized. A list of pre-specified AESIs is provided in Appendix 4.

PFIZER CONFIDENTIAL
Page 30

6.6.2. Laboratory Data

Descriptive statistics will be summarized by treatment group as well as mean change from baseline for laboratory parameters within SAS population.

Laboratory shift tables from baseline will be presented for the following laboratory abnormalities at baseline: D-dimer levels, Liver function tests (ALT/AST), Creatinine Clearance (derived using Cockcroft-Gault Equation), TSH, T4 (free), fibrinogen, platelets, PT, aPTT, albumin, and total proteins.

All laboratory data will be reported in accordance with Clinical Data Interchange Standards Consortium (CDISC) and Pfizer Standards (CaPS) for safety reporting.

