#### **Medical Conditions:**

- 1. History of hospitalization for the medical treatment of COVID-19.
- 2. Current need for hospitalization or anticipated need for hospitalization within 48 hours after randomization in the clinical opinion of the site investigator (see Section 8.1.2.)
- 3. Prior to current disease episode, any confirmed SARS-CoV-2 infection, as determined by a molecular test (antigen or nucleic acid) from any specimen collection.
- 4. Known medical history of active liver disease (other than nonalcoholic hepatic steatosis), including chronic or active hepatitis B or C infection, primary biliary cirrhosis, Child-Pugh Class B or C, or acute liver failure.
- 5. Receiving dialysis or have known moderate to severe renal impairment [ie, eGFR <45 mL/min/1.73 m^2 within 6 months of the screening visit, using the serum creatinine-based CKD-EPI formula].
- 6. Known HIV infection with a viral load greater than 400 copies/mL or taking prohibited medications for HIV treatment (from known medical history within past 6 months of the screening visit) (Appendix 8).

- 7. Suspected or confirmed concurrent active systemic infection other than COVID-19 that may interfere with the evaluation of response to the study intervention.
- 8. Any comorbidity requiring hospitalization and/or surgery within 7 days prior to study entry, or that is considered life threatening within 30 days prior to study entry, as determined by the investigator.
- 9. History of hypersensitivity or other contraindication to any of the components of the study intervention, as determined by the investigator.
- 10. Other medical or psychiatric condition including recent (within the past year) or active suicidal ideation/behavior or laboratory abnormality that may increase the risk of study participation or, in the investigator's judgment, make the participant inappropriate for the study.

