### 7.1.1. Potential Cases of Decreased eGFR

If postscreening eGFR is  $<45 \text{ mL/min}/1.73\text{m}^2$  the participant will be instructed to discontinue any remaining study intervention doses as soon as study staff become aware of the eGFR results.

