### 8.2.6. Clinical Safety Laboratory Assessments

See Appendix 2 for the list of clinical safety laboratory tests to be performed and the SoA for the timing and frequency. All protocol required laboratory assessments, as defined in Appendix 2, must be conducted in accordance with the laboratory manual and the SoA. Unscheduled clinical laboratory measurements may be obtained at any time during the study to assess any perceived safety issues.

Laboratory safety parameters will be graded according to the Division of AIDS (DAIDS) Table for Grading the Severity of Adult and Pediatric Adverse Events, version 2.1. The investigator must review the laboratory report, document this review, and record any clinically relevant changes occurring during the study in the AE section of the CRF. Clinically significant abnormal laboratory findings are those which are not associated with the underlying disease, unless judged by the investigator to be more severe than expected for the participant's condition.

All laboratory tests with values considered clinically significantly abnormal during participation in the study or within 28 days after the last dose of study intervention should be repeated until the values return to normal or baseline or are no longer considered clinically significant by the investigator or medical monitor.

If such values do not return to normal/baseline within a period of time judged reasonable by the investigator, the etiology should be identified and the sponsor notified.

See Appendix 6 for suggested actions and follow-up assessments in the event of potential drug-induced liver injury.

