# 10.2. Appendix 2: Clinical Laboratory Tests

The following safety laboratory tests will be performed at times defined in the SoA section of this protocol. Additional laboratory results may be reported on these samples as a result of the method of analysis or the type of analyzer used by the clinical laboratory, or as derived from calculated values. These additional tests would not require additional collection of blood. Unscheduled clinical laboratory measurements may be obtained at any time during the study to assess any perceived safety issues

Hematology	Chemistry	Other	Additional Tests (Needed for Hy's Law)
Hemoglobin	BUN or urea	Ferritin	AST, ALT (repeat)
Hematocrit	Creatinine a	hsCRP	Total bilirubin (repeat)
RBC count	Glucose	Procalcitonin	Albumin
Platelet count	Calcium	LDH	Alkaline phosphatase
WBC count	Sodium	CK	(repeat)
Total neutrophils	Potassium	Haptoglobin	Direct bilirubin
(Abs)	Chloride		Indirect bilirubin
Eosinophils (Abs)	Total CO 2 (bicarbonate)	Thyroid function	Creatine kinase
Monocytes (Abs)	AST, ALT	TSH	GGT
Basophils (Abs)	Total bilirubin	T4 (free)	PT/INR
Lymphocytes (Abs)	Alkaline phosphatase		Total bile acids
••••	Albumin		Acetaminophen drug
	Total protein	Coagulation	and/or protein adduct
	-	PT/aPTT	levels
		Fibrinogen	
		D-dimer	
		SARS-CoV-2	
		serology (IgM, IgG)	
		FSH b	
		Pregnancy test	
		(β-hCG) c	

 Table 1.
 Protocol-Required Safety Laboratory Assessments

a. eGFR will be calculated using the method developed by the CKD-EPI using serum creatinine.

b. FSH testing is performed locally for confirmation of postmenopausal status only.

c. Local urine testing will be standard for the protocol unless serum testing is required by local regulation or IRB/EC. Serum or urine  $\beta$ -hCG for female participants of childbearing potential.

The investigator must review the laboratory report, document this review, and record any clinically relevant changes occurring during the study in the AE section of the CRF.

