3.6.4. Laboratory Data

To determine if there are any clinically significant laboratory abnormalities, the hematological and clinical biochemistry and other safety tests will be assessed against the criteria specified in the Pfizer reporting standards. This assessment will take into account whether each participant's baseline test results are within or outside the laboratory reference range for particular laboratory parameter.

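### The SAP's only specified renal shift table uses Cockcroft-Gault clearance, so it cannot show who fell below the protocol's CKD-EPI eGFR limit of 45

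*SAP*

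**What the plan says.** **SAP.** Section 6.6.2 lists the laboratory parameters that get shift tables from baseline. The only renal entry is "Creatinine Clearance (derived using Cockcroft-Gault Equation". No shift categories are given and no weight basis is stated. The SAP mentions neither eGFR, CKD-EPI nor a limit of 45. The same section also plans general summaries: "Descriptive statistics will be summarized by treatment group as well as mean change from baseline for laboratory parameters within SAS population".

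**Protocol.** Table 1 in Appendix 2, footnote a, states that "eGFR will be calculated using the method developed by the CKD-EPI using serum creatinine". The limit of below 45 mL/min/1.73 m² appears in four places:

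- Exclusion criterion 5: "Receiving dialysis or have known moderate to severe renal impairment", with the limit applied "within 6 months of the screening visit, using the serum creatinine-based CKD-EPI formula".
- Exclusion criterion 18, which repeats the limit and the formula.
- Section 7.1.1: if eGFR after screening is below the limit, "the participant will be instructed to discontinue any remaining study intervention doses as soon as study staff become aware" of the result.
- The Schedule of Activities, which repeats that rule in its note on baseline laboratory samples.

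The last two name no formula, but the Appendix 2 footnote supplies it. Cockcroft-Gault does not appear in the protocol.

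**The concern.** A shift table exists to show who moved across a boundary that matters. Here the boundary that the protocol acts on is set in one measure, and the table is built on another. Cockcroft-Gault clearance is proportional to body weight and is not indexed to body surface area, whereas CKD-EPI eGFR is indexed and does not use weight. The trial enrols participants on the strength of a BMI above 25 (inclusion criterion 4), and SAP Section 6.4 plans a BMI ≥30 subgroup, so the trial expects participants in whom the two measures differ. A reader of the safety tables who wants to know how many participants per arm were below the protocol's limit, before or after dosing, could not get that from the table specified.

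**Working it through.** The plan states no figure on this point, so there is nothing to reproduce. The check is how far apart the two measures can be for a participant just below the limit.

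**Inputs from the documents.** The limit is 45 mL/min/1.73 m² by CKD-EPI (protocol criteria 5 and 18, Appendix 2). The shift table uses Cockcroft-Gault (SAP 6.6.2). Weight is recorded at screening (protocol 8.2.2).

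**Assumptions.** Neither equation is printed in the documents. I use their standard forms, actual body weight, and heights of 1.75 m for men and 1.62 m for women.

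- CKD-EPI 2009 without race term: eGFR = 141 × min(Scr/κ, 1)^α × max(Scr/κ, 1)^−1.209 × 0.993^age, × 1.018 for women; κ = 0.9 (men) or 0.7 (women). Creatinine exceeds κ throughout, so the α term equals 1.
- Cockcroft-Gault: CrCl = (140 − age) × weight / (72 × Scr), × 0.85 for women.

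**Step 1: creatinine that gives eGFR 44.**

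- Man aged 60, Scr 1.66: 141 × (1.66/0.9)^−1.209 × 0.993^60 = 141 × 0.477 × 0.656 ≈ 44.
- Woman aged 60, Scr 1.31: 141 × 1.018 × (1.31/0.7)^−1.209 × 0.993^60 = 143.5 × 0.469 × 0.656 ≈ 44.

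**Step 2: clearance for the same people** (creatinine unrounded).

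- Man: 80/(72 × Scr) = 0.667 mL/min per kg. At 80, 100 and 120 kg this gives 53, 67 and 80 mL/min. He passes 45 at 45/0.667 ≈ 67 kg and 60 at about 90 kg.
- Woman: 0.85 × 80/(72 × Scr) = 0.719 mL/min per kg. At the same weights this gives 58, 72 and 86 mL/min. She passes 45 at about 63 kg and 60 at about 83 kg.

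**Step 3: range over ages 30 to 85, both sexes, all at eGFR 44.**

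| BMI | Cockcroft-Gault, mL/min |
|---|---|
| 20 | 30.0 to 47.2 |
| 25 | 37.5 to 59.0 |
| 30 | 45.0 to 70.9 |
| 35 | 52.5 to 82.7 |
| 40 | 60.0 to 94.5 |

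The low end is the oldest participants and the high end the youngest.

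**Step 4: the opposite direction.** A woman aged 80 with BMI 20 (20 × 1.62² = 52.5 kg) and Scr 1.17 has eGFR 44 and clearance 60 × 52.5 × 0.85/(72 × 1.17) = 31.8. Above κ, eGFR varies as Scr^−1.209 and clearance as Scr^−1. At eGFR 60 her clearance is therefore 31.8 × (60/44)^(1/1.209) = 31.8 × 1.29 ≈ 41. She is well above the protocol's limit, yet her clearance is below 45.

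**Step 5: after the change.** A table on CKD-EPI eGFR with a cut at 45 places every participant below the protocol limit in the below-45 category by construction.

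**The case against.** The case against making much of this is good, and most of it stands as a limit on the point.

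- **No commitment is broken.** Protocol Section 9.3.6.1 promises only event frequencies and mean changes for laboratory data, and Section 9.3.6 plans no formal test. The choice of shift table is descriptive.
- **Other displays exist.** Creatinine is a protocol chemistry test and falls under the general summaries. SAP Section 6.6 plans standard tables and listings for laboratory parameters and treatment discontinuations. Participants stopped under Section 7.1.1 are not invisible. But means and mean changes do not show who crossed a limit, and no eGFR summary is specified.
- **Weight largely drops out of within-person change.** With one screening weight, relative change in Cockcroft-Gault follows creatinine. What differs is the category in which a participant is placed.
- **Display details are unknown.** Shift categories and weight basis are not given, and sponsor standards outside the documents may settle them.
- **The examples are hypothetical.** Nothing in the documents says how many participants would be near 45, in a trial that excludes known values below it and doses for 5 days.

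A reader might infer that treatment-emergent falls in renal function will be systematically under-displayed. The documents do not support that. Misplacement runs both ways (step 4), both arms use the same formula, and no between-arm bias is shown. Laboratory tests are generally not required at screening, and the Schedule of Activities attaches the rule to the baseline sample. Some values below 45 will therefore be pre-dose findings, not falls on treatment.

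**Conclusion.** The mismatch is in the current text of both documents and is worth correcting, as a small, cheap improvement to safety reporting. The specified renal shift table cannot show who was below the protocol's own limit. At eGFR 44 the tabulated quantity can lie anywhere from about 30 to 95 mL/min across BMI 20 to 40 and ages 30 to 85. That range rests on the assumed equation forms, actual body weight and the assumed heights. Eligibility, the discontinuation rule as applied and all efficacy analyses are untouched. No view is taken on which renal measure or limit is clinically right.

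Two wider readings are tempting and should not be drawn.

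- **Grading.** Protocol 8.2.6 says "Laboratory safety parameters will be graded according to the Division of AIDS (DAIDS) Table for Grading", while SAP 3.6.4 says laboratory tests "will be assessed against the criteria specified in the Pfizer reporting standards". A reader might infer that the protocol's Grade 3 and Grade 4 action rules lose their supporting tables. Those rules (Sections 7.1 and 10.1.5.1) act on adverse events that the investigator has judged related, with intensity graded under Section 10.3.3. They do not act on a laboratory grade alone. Whether the sponsor's standard outputs include graded laboratory tables cannot be known from these documents.
- **Liver.** The shift list names ALT/AST without bilirubin, although Appendix 6 uses both. A reader might infer that potential liver-injury cases would be missed. Appendix 6 has cases confirmed on repeat testing, with no other reason found, reported as SAEs. SAP 6.2.3 tabulates SAEs by arm, and bilirubin falls under the general summaries.

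**What to change.** Reconcile SAP Section 6.6.2 with the protocol by adding (or substituting):

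- a shift table on CKD-EPI eGFR, as defined in protocol Appendix 2, with 45 mL/min/1.73 m² as one category boundary;
- a by-arm count of participants with any value below 45, shown separately for pre-dose baseline and post-baseline samples. SAP Section 3.4 sets the laboratory baseline window as Day -2 to Day 1 regardless of clock time, so the table should say how the split is made.

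Keep the Cockcroft-Gault table as an additional display if it is wanted, and state its categories and weight basis.

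The cost is SAP wording and one extra table with its count. Creatinine, age and sex are already collected, and eGFR is already calculated under the protocol. Sites and participants are not affected.
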